## Research Protocol Lung Institute Dallas

Additional Exclusion Criteria for **ADIPOSE** Procedure

- Body Mass Index (BMI) less than 24  
*On a case-by-case basis, Provider may approve exceptions.*
- History of abdominal surgery with mesh;
- History of multiple abdominal surgeries;
- History of total abdominal liposuction and/or tummy tuck;
- History of Stents and Angioplasty;
- Atrial Fibrillation/Any Heart Arrhythmia;

- Congenital Heart Disease;
- Congestive Heart Failure (CHF)
- Cardiomyopathy
- History of heart attack (MI)
- History of stroke
- Coronary Artery Disease (CAD)

*On a case-by-case basis, Provider may approve exceptions.*

The Centers for Disease Control and Prevention has estimated National cardiovascular disease prevalence between 2011 to present at 4.1 %. The Texas Department of State Health Services has estimated the prevalence of Cardiovascular Disease and Stroke among adults to be:

- Texas 2010: 8.3 %
  - Dallas – Plano – Irving Primary Metropolitan Statistical Area 2007: 7.7 %
  - Denton 2007: 4.6 %
    - Collin County: 5.7 %
- History of blood clot (DVT & PE) on daily blood thinner
- Uncontrolled Diabetes;
- Neurodegenerative Diseases;
- Medication Rule Outs as follows:
  - Must be off Anticoagulation Drugs and other medications and/or substances that cause bleeding. (Must be held for an allotted time with prior approval from PCP/Prescribing Physician-specific hold times are subject to medication/substance type.)
  - Methotrexate (if unable to hold for 1 week prior to treatment)

#### Additional Exclusion Criteria for **BONE MARROW** Procedure

- Current blood thinner for any type of existing heart condition;
- Osteoporosis;
- Bilateral hip replacement;
- Radiation of pelvis area (including prostate seed implants)
- Uncontrolled Diabetes;
- Medication Rule Outs as follows:
  - Must be off Anticoagulation Drugs and other medications and/or substances that cause bleeding. (Must be held for an allotted time with prior approval from PCP/Prescribing Physician-specific hold times are subject to medication/substance type.)
  - Methotrexate (if unable to hold for 1 week prior to treatment)

## 10. STUDY OUTCOMES

The anticipated outcomes of this study are a minimization of adverse events, an improvement in pulmonary function testing (measured by FEV1), and an improvement in self-reported quality of life indicators.

Rev\_2/5/16 Page 5 of 10

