## **3. AIM(S) OF STUDY**

Through the collection of qualitative and quantitative data, Lung Institute aims to explore and describe the safety and efficacy of autologous stem cell treatment for chronic lung disease with dissemination to the public and to the medical community for the advancement of regenerative medicine. The study aims to confirm the safety of autologous cell therapy, explore the effect of autologous cell therapy treatment on pulmonary function, and to describe the anecdotal quality of life changes of patients following treatment using both quantitative and qualitative measures.

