## **5. HYPOTHESES**

### **5a. Primary Hypothesis/Quantitative Arm**

Null hypothesis: Following autologous stem cell treatment for chronic lung disease, patients will have no improvement in pulmonary function (measured by FEV1) at six months

Alternative hypothesis: Following autologous stem cell treatment for chronic lung disease, patients will have an increase in pulmonary function (measured by FEV1) of 5 to 10% or more

Rev\_2/5/16 Page 2 of 10

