### **5c. Qualitative Arm**

An assumption of qualitative research is that no pre-determined hypothesis is made. Following autologous stem cell treatment for chronic lung disease, patients will report improvement in at least one of several quality of life indicators.

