## 6. STUDY DESIGN

This study uses a concurrent mixed-methods approach to collect and analyze both qualitative and quantitative data. The *quantitative* arm will use a non-experimental, descriptive approach to measure and analyze pre- and post-stem cell treatment pulmonary function test results of treated patients. Measurement of the occurrence of adverse events will also be part of the quantitative arm.

Pre-treatment pulmonary function test results (measured by FEV1) will be compared with a six-month post-treatment pulmonary function test result (FEV1) for each patient. The aim of this method is to generalize an improvement in pulmonary function (measured by FEV1) among the general population of all individuals treated by autologous cell therapy for chronic lung disease.

The *qualitative* arm of the study uses an interpretive phenomenological approach to collect and analyze pre- and post- cell therapy anecdotal data regarding perceived quality of life among treated patients. Phenomenological research involves investigating the lived experience.

Qualitative research has several assumptions (D. Nicholls, 2009; Ritchie & Lewis, 2003). Primarily, there is no predetermined theoretical framework- rather the theory, if any, is derived from the data. Secondly, qualitative research is context-driven. Finally, qualitative researchers focus on the *emic* perspective that concerns itself with the view, perspectives and descriptions of others.

This study uses an *interpretive phenomenological analysis* (IPA) approach throughout the study from planning to data collection to analysis. This methodology is used to illuminate each participant's variation of the same general phenomenon (in this case, COPD) (Reissman, 2008; Ritchie & Lewis, 2003).

Data from both arms of the study will be combined following data collection for analysis, discussion and presentation. Safety data on adverse outcomes will be tracked and reported separately as a descriptive, quantitative analysis.

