### **12b. Statistical methods**

For the quantitative, descriptive arm of this study, sample characteristics will be collected to include age, sex and diagnosis. Pre- and post-treatment FEV1 measurements will be collected on each patient and evaluated by simple measures of central tendency (mean, median and mode). Sufficient descriptive data will be collected and reported to encourage replication of our study.

For the qualitative, anecdotal arm of the study, Lung Institute utilizes CCQ, the Clinical COPD Questionnaire to document patient's perceptions on improved quality of life. The information will be collected and interpreted by evaluating for common themes within the anecdotes. As a note regarding the rigor of qualitative research: is important in qualitative research to ensure that the study is credible and trustworthy (Smith, Flowers and Larkin, 2009). A number of guidelines for assessing this quality look toward establishing credibility. Psychologist Lucy Yardley's work in 2000 provides the principles for assessing the quality of qualitative research and how the interpretive phenomenological method can address them. First, the study must provide good *sensitivity to context*. In this study, the immersion in the clinic through field experience, the existing literature on COPD and stem cell treatment, and the anecdotes obtained

Rev\_2/5/16 Page 7 of 10

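### No count of patients whose FEV1 or CCQ worsens is pre-specified, and no measured decline is linked to the safety question

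*Combined protocol and SAP*

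**What the plan says.** Section 10 names three anticipated outcomes: few adverse events, and "an improvement in pulmonary function testing (measured by FEV1), and an improvement in self-reported quality of life indicators". The hypotheses point the same way. The null in 5a is that "patients will have no improvement in pulmonary function (measured by FEV1) at six months"; the alternative is that "patients will have an increase in pulmonary function (measured by FEV1) of 5 to 10% or more". Section 5c expects that "patients will report improvement in at least one of several quality of life indicators".

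The analysis is brief. Section 6 says that the pre-treatment FEV1 "will be compared with a six-month post-treatment pulmonary function test result (FEV1) for each patient", and 12b says that the measurements will be "evaluated by simple measures of central tendency (mean, median and mode" being the last item listed. The CCQ is read for common themes. No SD, interval, distribution of change or count of patients who worsen is planned for either measure.

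On safety, section 6 states: "Safety data on adverse outcomes will be tracked and reported separately". Section 11 collects adverse events and quality of life at 2 weeks, 3 months and 6 months, by calls in which participation is voluntary. No section sets a threshold for FEV1 or CCQ worsening, or says that a measured decline bears on research question 1 (is the treatment safe?).

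**The concern.** A patient whose FEV1 falls by 15% and a patient whose FEV1 does not move have the same status under 5a: not improved. Under 5c, a patient who is better on one indicator and worse on all the others meets the stated expectation. The planned FEV1 summaries give the centre of the values and say nothing about how many patients lie well below their own baseline.

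Two things are at stake. Section 13 lists respiratory difficulties and emboli among the risks, yet FEV1, the only lung-function measure named as a study tool in 11c, has no stated part in answering the safety question. And a gain of 5 to 10% or more, as worded in 5a and in the benefits list of section 13, could easily be presented as a number of patients who reached it. Section 2 reports the pilot in that form, as an 84 percent response rate, without the number who got worse. Such a count cannot be interpreted unless the matching count of falls stands next to it.

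**Working it through.** **Plan's own figure.** Section 12a anticipates 200 patients and gives no alpha, power, SD or dropout, so 200 cannot be reproduced. It therefore implies no SD of FEV1 change that could be used below.

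**What each rule does with a decline.**
- 5a null: an unchanged patient and a patient 15% lower are classed alike.
- 5c: one indicator up and the rest down counts as improvement.
- 12b, FEV1: declines enter the mean and median, but no spread or count is shown.
- 12b, CCQ: themes only; no scored change and no category for worse.
- Sections 6 and 11, safety: adverse events are reported separately; an FEV1 or CCQ decline is not defined as one.

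**How many patients cross 5% with no true change.** Inputs: n = 200 (12a) and thresholds of 5% and 10% (5a, section 13). Assumed: percent change in FEV1 is normal with mean 0, its SD is 5, 10, 15 or 20% of baseline, and all 200 have a six-month value.

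Formula: P(change ≥ +t) = 1 − Φ(t/SD). By symmetry the same share has a change ≤ −t.

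| SD | 5/SD | P(≥ +5%) | Expected of 200 (95% binomial range) | P(≥ +10%) | Expected of 200 |
|---|---|---|---|---|---|
| 5 | 1.00 | 15.9% | 32 (22–42) | 2.3% | 5 |
| 10 | 0.50 | 30.9% | 62 (49–75) | 15.9% | 32 |
| 15 | 0.33 | 36.9% | 74 (61–87) | 25.2% | 50 |
| 20 | 0.25 | 40.1% | 80 (67–94) | 30.9% | 62 |

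The same numbers would be at −5% and −10%.

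**If the mean change is not zero.** Section 1 describes a natural decline in COPD. With an assumed mean of −2%, the share reaching +5% is 1 − Φ(7/SD) and the share at −5% or lower is Φ(−3/SD). For SD 5, 10, 15 and 20, that is 16, 48, 64 and 73 rises against 55, 76, 84 and 88 falls.

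**What a favourable mean can hide.** With an assumed mean of +5%, the share falling by at least 5% is Φ(−10/SD): 2.3%, 15.9%, 25.2% and 30.9%, or 5, 32, 50 and 62 of 200. A report of mean, median and mode would not distinguish these cases.

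**The case against.** The strongest reply is that a directional hypothesis does not discard declines. Section 3 states a neutral aim, to "explore the effect of autologous cell therapy treatment on pulmonary function"; section 6 compares values for each patient; and every decline pulls the mean down. Clinical deterioration also has a route into the safety data: adverse events are sought at three time points, escalated internally and reported to the IRB (section 11), and respiratory difficulties are a listed risk (section 13). All of this stands. A reader might infer that the protocol looks only for improvement and counts worsening nowhere as harm; the documents do not support that. What is missing is narrower: a rule that makes a measured FEV1 or CCQ decline visible or connects it to safety.

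A reader might also infer that a count of patients gaining 5% is planned. It is not. Section 12b plans none, and 5a does not say whether 5 to 10% is a group mean or a per-patient threshold, so the table above applies only to the per-patient reading. Nor is FEV1 the only objective measure: the follow-up section of policy CL-005 also advises oximetry and a six-minute walk test at six months, although section 10 names neither as an outcome.

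The size rests on assumptions. At SD 5 the share is 16%, about half that at SD 10. A six-month SD contains real change in disease as well as measurement error, so the variation is not all noise in the instrument. Equal numbers on both sides require a mean change of zero.

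Finally, calling every 5% fall a harm would repeat the same mistake in the other direction, because variation alone produces many such falls. That is correct, and the fix respects it.

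**Conclusion.** The point holds in this form: no count of patients who worsen on FEV1 or CCQ is pre-specified, no measured decline is tied to research question 1, and the planned FEV1 summaries show no spread. The study could therefore report improvement, on the mean or on any single quality-of-life indicator, while a material share of patients deteriorates.

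On a per-patient reading of 5 to 10%, between 32 and 80 of 200 patients (16% to 40%) would reach +5% with no true change, and as many would be at −5%. This assumes an SD of 5 to 20% of baseline, normality, a zero mean change and complete six-month data, none of which the documents supply. The gap in the plan does not depend on these figures.

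Two further inferences are tempting and fail. An FEV1 fall of 5% does not by itself show treatment harm. An excess of rises over falls does not show benefit: there is no control group, natural decline could shift the balance one way, and the pulmonary rehabilitation recommended after treatment in CL-005 could shift it the other.

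**What to change.** In sections 10 and 12b:
- Report paired FEV1 change with its SD and 95% CI.
- Add one table with the number and percent of patients with a rise and with a fall of at least 5% and at least 10%, and the number missing at six months.
- State whether 5 to 10% in 5a is a group mean or a per-patient threshold, and whether it is relative to baseline.
- In place of the any-one-indicator reading of 5c, give better/unchanged/worse counts for the CCQ score and for each indicator. The cut-offs must be set in advance, since the documents give none. The thematic analysis can remain as it is.
- Show the FEV1 falls descriptively next to the adverse-event results under research question 1, without labelling each fall as treatment harm.
- State that, without a control group, neither the rises nor their excess over the falls establishes a treatment effect.

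The cost is one extra table, from measurements that the plan already calls for, and a headline that may look less favourable.

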**Research Protocol**  
**Lung Institute Dallas**

## 11. STUDY PROCEDURES

Informed Consent Form is obtained. Consent form must be complete, signed, and dated without forgeries or alterations. Information should be delivered in a manner in which the Patient and/or the patient's legal representative could reasonably be expected to understand.

A review of the patient's medical record will be conducted to approve for treatment. Approved treatment plans will be documented in the patient's electronic medical record. Medical records obtained from external providers will be kept in the patient's medical record and must include recent laboratory data, results of any outside office notes, chest x-ray results and any relevant information as required per treatment inclusions and exclusions protocol.

Prior to Bone Marrow aspiration, Adipose extraction, and Venous stem cell administration, the clinician will perform a physical assessment. Attached are the following Standard Operating Procedures (SOPs) for each type of cell therapy that Lung Institute provides to qualified candidates:

- Venous Procedure
- Adipose Extraction Procedure
- Bone Marrow Aspirate Procedure

Patient follow-up may be conducted at the Lung Institute facility or may be completed by telephone at 2 weeks, 3 months and 6 months post-treatment to measure adverse events and quality of life. Patient participation in these phone calls is voluntary. Data collected at these time points will be entered into password-protected database for data management and reporting. Patients will be issued a journal during their treatment to record quality of life indicators from the time they are discharged from the clinic until they are called for follow-up. This allows the patients to better recall how they felt/are feeling to better communicate progress during follow-up appointments/calls.

Patients will have pulmonary function testing 6 months post-treatment. This will be done at the Lung Institute facility, or by their primary care physician, or pulmonologist.

All adverse events are reported to the Principal Investigator. The Medical Director and Compliance Department are notified within 24 hours for appropriate follow-up. These events are documented in the patient's medical record. Additionally, adverse events will be reported to the Quality Improvement & Risk Management (QI&RM) Committee for interdepartmental transparency and to meet internal and external reporting requirements. Per MaGil IRB Investigators Handbook §5- Investigator Responsibilities, the IRB will be notified within 5 days from the PI becoming aware of any adverse events requiring immediate intervention to prevent serious harm, and within 10 days for any problem or unanticipated occurrence.

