## **H. FOLLOW-UPS**

1. LI CONDUCTS A FOLLOW-UP EVALUATION VIA A TELEPHONE CALL AT 2 WEEKS.
  - a) TWO CALL ATTEMPTS ARE MADE.
2. LI CONDUCTS AN ADDITIONAL FOLLOW UP PHONE CALL CONDUCTED AT 12 WEEKS.
  - a) TWO CALL ATTEMPTS ARE MADE.
3. PATIENT IS ADVISED TO RETURN TO CLINIC AT 6 MONTHS FOR EVALUATION, LABS, PULMONARY FUNCTION, PULSE OXIMETRY AND SIX MINUTE WALK TEST.
  - a) IF RETURN TO CLINIC IS NOT POSSIBLE DUE TO DISTANCE, THE PATIENT IS ADVISED TO GO TO A LOCAL PHYSICIAN FOR EXAMINATION, LABS, PULMONARY FUNCTION, PULSE OXIMETRY, AND SIX-MINUTE WALK TEST AT 6 MONTHS.
  - b) TWO CALL ATTEMPTS ARE MADE TO OBTAIN PATIENT PROGRESS VIA A QUALITY OF LIFE SURVEY.

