**PATIENT CHECK-IN**

2. Is today the first treatment day for the Patient?
- **If NO** > Skip to Step 5 of this SOP
  - **If YES** > Proceed to Step 3 of this SOP

3. Office Manager receives Patient and processes paperwork and completes Patient Flow Chart as required.
- Has Office Manager reviewed and collected the required registration paperwork below, as well as assists the Patient with any remaining paperwork required for processing?
    - ✓ New Patient Packet (If NPP completed via Portal; OM must obtain hard copies of forms e and f)
      - a) Personal Information;
      - b) Emergency Contact Information;
      - c) Referral Source;
      - d) Medical History;
      - e) Authorization to Verbally Discuss Health Information;
      - f) Patient Bill of Rights;
      - g) How to File a Complaint; and
    - ✓ Provided the Patient with LI Privacy and Security Practices Notice
    - ✓ Consent Form Review and Completion; and
    - ✓ Quality of Life Survey
- **If NO** > Must complete this Step prior to moving forward.
  - **If YES** > Proceed to Step 4 of this SOP

10Mar2016 - version 2.0

LI-001

4. Office Manager processes payment.
- Has Office Manager collected and processed payment by completing the following?:
    - ✓ Obtaining a signed Payment Agreement;
    - ✓ Providing invoice and copy of payment agreement to Patient; and
    - ✓ Note payment in required systems (both EMR and CRM)
- **If NO** > Must complete this Step prior to moving forward.
  - **If YES** > Proceed to Step 5 of this SOP

5.	
Office Manager updates EMR as required.
 
 
• Has Office Manager scanned any required paperwork (e.g.: Registration, Payment Agreement) into the EMR chart; and
 
• Completed the following EMR steps? 
 
✓ Patient Check-In
 
✓ Exam Room
 
 
 
 
➤ If NO > Must complete this Step prior to moving forward.
 
➤ If YES > Proceed to Step 6 of this SOP

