6.	
Office Manager completes Patient Flow Chart and transfers Patient to Clinical Staff.
 
 
• Has Office Manager completed the following? 
 
✓ Signed-off on the Patient Flow Chart; and
 
✓ Brought the Patient back to assigned exam room?
 
 
 
 
➤ If NO > Must complete this Step prior to moving forward.
 
➤ If YES > Patient Check-In Process completed; pick-up on Step 7 to complete Check-Out Process.

PATIENT CHECK-OUT	
7.	
Is today the Patient's discharge day?
 
➤ If NO > Skip to Step 11 of this SOP
 
➤ If YES > Proceed to Step 8 of this SOP

8.	
Office Manager provides Patient with Satisfaction Survey and Doctor's letter of treatment.
 
 
• Has Office Manger completed the following discharge steps? 
 
✓ Patient is given instructions to complete Satisfaction Survey and Media Release to hand back to Office Manager prior to departure;
 
✓ Is provided with correct Doctor's letter of LI treatment completed; and
 
✓ Completed Patient Flow Chart & Scan into EMR.
 
 
 
 
➤ If NO > Step must be completed prior to moving forward.
 
➤ If YES > Proceed to Step 9 of this SOP

9.	
Office Manager obtains Media Release and Patient photo, if Patient is in agreement.
 
 
• Has the Office Manager obtained the following? 
 
✓ Patient Testimonial Authorization Form (if Patient is in agreement); and
 
✓ Taken a photo of Patient for approved use.
 
 
 
 
➤ If NO > Step must be completed prior to moving forward.
 
➤ If YES > Proceed to Step 10 of this SOP

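### Quality of life is not collected in a matched way before and after treatment, so part of any pre-post change may reflect how it was collected

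*Combined protocol and SAP*

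**What the plan says.** Section 6 (Study Design) says that the qualitative arm will "collect and analyze pre- and post- cell therapy anecdotal data regarding perceived quality of life among treated patients". Perceived quality of life is the third research question (section 4) and one of the three outcomes in section 10. Section 12b names the CCQ as the instrument and plans to read the replies for themes. Section 2a states that there is no control group, and section 11b that nobody is masked.

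**Before treatment.** Step 3 of the Office Manager SOP, on the first treatment day, asks: "Has Office Manager reviewed and collected the required registration paperwork below", and continues "as well as assists the Patient with any remaining paperwork required for processing". The list ends with the "Quality of Life Survey". Payment is Step 4.

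**At discharge.** Steps 8 and 9 of the same SOP hand the patient a satisfaction survey and a media release, then seek a "Patient Testimonial Authorization Form (if Patient is in agreement") and a photo.

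**After treatment.** Section 11 measures quality of life at 2 weeks, 3 months and 6 months, at the facility or by telephone, and the calls are voluntary. Policy CL-005, section H, item 3b says of the 6-month point: "TWO CALL ATTEMPTS ARE MADE TO OBTAIN PATIENT PROGRESS VIA A QUALITY OF LIFE SURVEY". Its entries for 2 and 12 weeks are telephone calls and name no such survey. On the journal, section 11 says: "Patients will be issued a journal during their treatment to record quality of life indicators from the time they are discharged from the clinic". Its stated purpose is to help patients remember and report how they have felt. Step 24 of the Venous SOP and Step 19 of the Discharge SOP have staff go over the journals as a source of quality-of-life outcome data.

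**The concern.** A self-reported outcome in an unmasked, single-group study is sensitive to how the question is put. If mode, recall aid and circumstances change between the two measurements, the change in score or in narrative contains the change of method as well as any change in the patient. A control group questioned in the same way could cancel that component, but this design has none. A larger sample would not remove it either, because the shift is systematic.

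The stake is the answer to research question 3. Section 5c sets a low bar, improvement in any one of several indicators, and section 3 intends the findings for the public and the medical profession. A modest pull on some answers could therefore reach the published conclusion.

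**Working it through.** **Step 1. The plan's own figure.** The only planning number is the anticipated 200 patients (section 12a). It comes with no effect size, standard deviation, error rate, power or dropout, so it can be neither reproduced nor refuted. It is not in dispute here. The point is about measurement, so the passages are set side by side.

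| Feature | Baseline | Follow-up | Matched? |
|---|---|---|---|
| Instrument | Quality of Life Survey; CCQ named in 12b | Quality of life survey; CCQ named in 12b | Probably, but not stated |
| Mode | In the check-in paperwork, staff help available | Facility or telephone | Not for telephone patients; unclear for facility patients |
| Collecting organisation | The clinic | The clinic | Yes |
| Journal | None yet | Kept from discharge onward | No, for any patient |
| Media release, testimonial and photo already requested | No | Yes | No |
| Mode recorded or analysed | Not mentioned | Not mentioned | No provision |

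Three features differ: mode (for some patients), recall aid (all patients) and the prior media requests (all patients are asked; agreement is optional).

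**Step 2. How large a shift would matter.** The documents give no size, so this is an illustration on assumed inputs. Suppose quality of life were scored and tested as a mean paired change, two-sided 5% level, with no true change and a systematic method shift of *b* standard deviations (SD) of change. Section 12b plans no such test.

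- 95% confidence interval half-width at n = 200: 1.96/√200 = 0.139 SD.
- Chance of a nominally significant improvement: 1 − Φ(1.96 − b√n).
- Example, n = 200 and b = 0.1: b√n = 1.414; 1.96 − 1.414 = 0.546; 1 − Φ(0.546) = 29.3%.

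| Assumed b (SD) | n = 200 | n = 100 responders |
|---|---|---|
| 0 | 2.5% | 2.5% |
| 0.05 | 10.5% | 7.2% |
| 0.1 | 29.3% | 16.9% |
| 0.2 | 80.7% | 51.6% |
| 0.3 | 98.9% | 85.1% |

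If the shift affected only telephone answers and half were by telephone, the mean shift would be b/2. A telephone shift of 0.2 SD would then act roughly like the 0.1 row. The range 0 to 0.3 SD is an assumption.

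**The case against.** A reader might infer more than this: that the baseline is free of pressure while follow-up answers are spoken to a paid provider by patients who have agreed to a public testimonial, so that the change is inflated upward. The documents do not support that.

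- The same clinic collects the baseline, with staff help available and payment as the next step. Neither payment nor the collecting organisation is new at follow-up.
- The testimonial is optional, and no document says how many agree. Only the request reaches everyone.
- The sign of a telephone-versus-form difference is not given, and a journal that sharpens recall could move answers either way.
- Patients followed at the facility may complete the survey just as they did at baseline.

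Nor is it right that the comparison has no pre-treatment side. A survey is taken before treatment, and section 12b names one instrument. Only the journal is one-sided.

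It can also be said that section 11c refers to an attached questionnaire, absent from the text available here, which may state how it is completed. A further argument is that an uncontrolled, unmasked, thematic outcome cannot support attribution to treatment in any case, so this adds little.

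These arguments narrow the point but leave its core. An instruction on the form could settle the mode, but not the journal's starting date or the order of the media requests. Nor is the journal only a recall aid, since two SOPs treat it as outcome data. A weak design is also no reason to leave an avoidable mismatch in a stated outcome.

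**Conclusion.** The point holds in limited form. Collection of quality of life is not matched before and after treatment. With no control group or masking, part of any pre-post change may reflect the method. The documents fix neither the size nor the direction of that part. The request for a testimonial, media release and photo plausibly favours positive answers, but this is an inference and not a measured effect. The figures in the working show only that, if the outcome were tested, a shift of 0.1 to 0.2 SD would matter at n = 200. They rest on an assumed shift, an assumed test and complete response.

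The change should be made before enrolment, because an unrecorded mode and missing pre-treatment entries cannot be recovered later. The FEV1 comparison is not touched by this point.

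**What to change.** - **(a) One form, one mode.** Have the patient self-complete the same CCQ form, on paper or through the existing portal, at baseline, 2 weeks, 3 months and 6 months, before looking at the journal. Allow telephone completion as a fallback, record it, and also show results by mode. Keep the calls for safety and for the qualitative interview described in section 12b, held after the form is done. Align CL-005 section H with section 11 on which contacts collect the survey.
- **(b) Media requests later.** Move the media release, testimonial and photo (Office Manager SOP, Steps 8 and 9) to after the 6-month survey has been received. The rest of Step 8 can stay.
- **(c) Journal.** Either send it once the patient is approved, early enough for entries before the first treatment day, or report journal material as post-treatment only and not as pre-post change. Handing it out with the registration packet would not be enough, because that packet is collected on the first treatment day.

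The cost is some extra reminders, possibly a few more missing forms, and testimonials obtained about six months later. The form and the journal are already in use. Even after these changes, the quality-of-life change should be described as uncontrolled and unmasked.
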